- Male partner sterilization prior to the female subject's entry into the study, and this male is the sole partner for that subject [Hatcher, 2007a]. The information on the male sterility can come from the site personnel's: review of subject's medical records; medical examination of the subject and/or semen analysis; or interview with the subject on his medical history.
- Combined (oestrogen and progesterone containing) hormonal contraception associated with the inhibition of ovulation***:
 - Oral
 - Intravaginal
 - Transdermal
- Bilateral tubal occlusion

* A Woman of childbearing potential (WOCBP) is defined as any female who has:

- Experienced menarche
- Not undergone surgical sterilization (hysterectomy , bilateral salpingectomy or bilateral oophorectomy)
- Not experienced menopause. Women are considered menopausal if they have not had a menses for at least 12 months and have an FSH (follicle stimulating hormone) of greater than 40 IU/L or, if FSH testing is not available, they have had amenorrhea for 24 consecutive months**.

**Females treated with hormone replacement therapy, (HRT) are likely to have artificially suppressed FSH levels and may require a washout period in order to obtain a physiologic FSH level.

***If a patient is randomised to Syntuza, an alternative highly effective method of contraception should be used

APPENDIX 8 – SAFETY REPORTING FLOW CHART

Safety Data	Reporting Format	Timelines
All SAEs arising during the Clinical Trial, regardless of Investigator/designee causality assessments against IMP(s)	SAE form	Site to report to sponsor within 24 hours of first becoming aware of the event. Sponsor to report to Funder within 24 hours of awareness.
Pregnancy information for all female Clinical Trial Subjects who become pregnant while participating in the Clinical Trial and following exposure to an IMP. The subject will also be followed to determine the outcome of the pregnancy (including information on the status of the mother and child), which will also be reported to sponsor.	Copies of the original Pregnancy CRF pages	Site to send to sponsor within 24 hours of first becoming aware of the pregnancy or the pregnancy outcome. Sponsor to report to Funder within 24 hours of awareness.
Deaths	Any AE, AR or unexpected AR that results in death should be reported as an SAE on an SAE form.	Site to report to sponsor within 24 hours of first becoming aware of the event. Sponsor to report to Funder within 24 hours of awareness.
Overdose	If the overdose fits the criteria of an SAE (see Section 8) it should be reported appropriately on an SAE form, else report as a Special Reporting Situation.	Site to report to sponsor within 24 hours of first becoming aware of the event. Sponsor to report to Funder within 24 hours of awareness.
Special Reporting Situations: (See section 8.10)	Email	Site to report to sponsor within 24 hours of first becoming aware of the event. Sponsor to report to Funder within 24 hours of awareness.
Product Quality Complaints	Email	Site to report to sponsor within 24 hours of first becoming aware of the event. Sponsor to report to Funder within 24 hours of awareness.

APPENDIX 9 – AMENDMENT HISTORY

Comparative table with Description of Change and Rationale for change to the Protocol from Version 2.0 to Version 4.0.

Please note version 3.0 was never fully approved in any territory as it did not include changes approved between versions 1.5 and version 2.0. V4.0 re-incorporates all approved changes made previously and also includes the following:

Change No.	Description of Change	Rationale for Change
1.	Changes made to reference the compliance with Clinical Trial Regulation (EU) No 536/2014 in the statements the CI, Sponsor, statistician, and PIs sign. Addition of EUCT number to title page.	Compliance with Clinical Trial Regulation (EU) No 536/2014
2.	Protocol summary: Number of sites and countries changed from 45 to 61, and 7 to 11, respectively.	Expansion of trial sites and territories is ongoing.
3.	Section 1.2.1: Therefore, in cases when needs ART needs to be initiated before genotypic testing results are available	Typographical error on in the background and rationale section
4.	Section 1.2.1, Section 7.1 and Section 7.7: Change to the language regarding the referenced RSI provided by the sponsor in	Changed to emphasize that the study team should refer to the particular SmPC provided and authorised as the RSI in the study, even if this is not the local country version or most current.
5.	Section 5.2: Exclusion Criteria: Removal of the requirement that forbidden concomitant medications should have been stopped at least 30 days ahead of baseline.	30 days was added initially at the start of the trial when there was less safety data available for Biktarvy, in particular, as it was not yet authorised when the protocol was written. Therefore, it was thought to exclude all contraindicated medication for 30 days as a safety precaution. However, it is now thought this is unnecessary and the sites should follow any recommendations in the SmPC.
6.	Section 5.2 and Appendix 1: A latent TB test may be performed. Previously a TB test will be performed	To clarify that the test is to confirm if latent TB is present. Additionally, TB testing has always been intended to be done in those patients in who it may be suspected. This wording has been changed to clarify that.
7.	Removal of “Investigator Brochure” from the title of section 7.1	There is no Investigator Brochure used for the trial.
8.	Section 8.2.4 and Section 8.3.3.:	Addition in line with change to Sponsor’s safety event reporting form

Change No.	Description of Change	Rationale for Change
	1. Additional text to state that details of reporter included on the Safety Event Report Form 2. Addition of text to mention the pharmacovigilance management plan (PVMP) will be used by the CI and sponsor in assessment of safety reporting	to include the pharmacovigilance management plan (PVMP).
9.	Section 8.2.4 Recording and Reporting of SAEs and SUSARs Statement made that the Sponsor will update the Eudrvigilance database.	Compliance with Clinical Trial Regulation (EU) No 536/2014
10.	Section 8.3.6 and Section 12 Addition of details regarding Endpoint committee review	An endpoint committee may be requested ahead of any data analysis required by the DSMB or the TSC.
11.	8.8 Development Safety Update Reports Statement of intent for the sponsor to submit a single safety report for both IMP	Compliance with Clinical Trial Regulation (EU) No 536/2014
12.	9.5 Interim analysis and criteria for the premature termination of the trial Statement that there are no specific trial stopping criteria	Compliance with Clinical Trial Regulation (EU) No 536/2014
13.	13.3 Regulatory Compliance Change to reflect the trial will be conduct in compliance with Clinical Trial Regulation (EU) No 536/2014	Compliance with Clinical Trial Regulation (EU) No 536/2014
14.	13.6 Data protection and patient confidentiality Updated to comply with the Clinical Trial Regulation (EU) No 536/2014	Compliance with Clinical Trial Regulation (EU) No 536/2014
15.	Section 13.5: Change to the definition of serious breach and reporting timelines	The previously included strictly MHRA definition has hence been modified to include the Clinical Trial Regulation wording.
16.	Appendix 1: Study Flowchart Removal of “including urinary chemistry” after “Clinical Chemistry” in the description of this assessment	The words are superfluous as the actual tests required are described in the footnote 12 – removing them for clarity for the sites.
17.	Appendix 1: Change to the footnote 10 wording after the asterisk: regarding when assessments should be taken. Changing from “after baseline” to “at all visits required”	Changing this for clarity as it is ambiguous about whether urinalysis assessments should be done at all visits.

HIV-1	Human Immunodeficiency Virus Type-1
IAS	International AIDS Society
ICH	International Conference on Harmonisation of technical requirements for registration of pharmaceuticals for human use
IGRA	Interferon-Gamma Release Assays
IMP	Investigational Medicinal Product
INI	Integrase Inhibitor

INSTI	Integrase Strand Transfer Inhibitor
IRIS	Immune Reconstitution Inflammatory Syndrome
ITT	Intent-to-Treat
LOCF	Last Observation Carried Forward
MedDRA	Medical Dictionary for Regulatory Activities
NNRTI	Non-Nucleoside Reverse-Transcriptase Inhibitor
NRTI	Nucleoside Reverse-Transcriptase Inhibitor
OI	Opportunistic Infection
PI	Protease Inhibitor
QD	queaque die (once daily)
QOL	Quality of Life
RAL	Raltegravir
RNA	Ribonucleic Acid
RT	Reverse Transcriptase
SAE	Serious Adverse Event
SD	Standard Deviation
SOP	Standard Operating Procedure
SUSAR	Suspected Unexpected Serious Adverse Reaction
TAF	Tenofovir Alafenamide Fumarate
TDF	Tenofovir Disoproxil Fumarate
TB	Tuberculosis
TFV	Tenofovir
US	United States

1. INTRODUCTION

1.1 PREFACE

The effectiveness of HIV antiretroviral therapy (ART) has consistently improved over the years. This is due to novel compounds and combinations with improved antiviral efficacy and side effect profiles resulting in less virologic failures and treatment discontinuation. On the other hand, most recent randomised controlled trials for first line treatment consider patients with less advanced disease (mean CD4 cell counts at baseline $>350/\mu\text{l}$, less than 15% of patients with CD4 cell counts $<200/\mu\text{l}$) and low baseline viral loads (DeJesus *et al.*, 2012) (Raffi *et al.*, 2013) (Walmsley *et al.*, 2013) (P.E. Sax *et al.*, 2017) (Gallant *et al.*, 2017). This favours superior overall response rates, as these patients usually suffer from less co-morbidity, drug-drug interactions (DDI), and other risks for treatment failure. The rate of patients with acquired immunodeficiency syndrome (AIDS) recruited into these trials was low, while a third of HIV-positive patients are diagnosed late in the course of the disease (CD4 T-cell count $<200 \text{ cells/L}$ or presence of AIDS) (Raffetti *et al.*, 2016) (Sobrino-Vegas *et al.*, 2012). Much less is known about which ART regimens perform best in late presenters in terms of viral efficacy, immune reconstitution, improvement of AIDS-related co-morbidities and adverse events (AEs). No specific combinations have been compared in sufficiently powered randomised clinical trials, and all regimens considered in international guidelines for first line therapies are judged as equal standard of care for these patients. Initially, protease inhibitor (PI) containing regimens were frequently used in patients presenting late or with AIDS defining events (Mussini *et al.*, 2008).

However, specifically regimens containing integrase inhibitors (INI) are promising candidates for treatment combinations in patients with CD4 cell counts $<200/\mu\text{l}$ due to their antiviral activity and rapid decline of viral load, beneficial side-effect profile and metabolism pathways compared to other regimens. Also, integrase inhibitors such as dolutegravir (DTG) and bictegravir (BIC/B) have high genetic barriers, thereby preventing resistance mutation development and ensuring sufficient antiviral activity in case of pre-existing mutations against nucleosides (Demarest *et al.*, 2018). Therefore, in cases when needs ART to be initiated before genotypic testing results are available, current European AIDS Clinical Society (EACS) Guidelines (EACS Treatment Guidelines 9.0) recommend to include a drug with a high genetic barrier to resistance in the first-line regimen (e.g. PI or DTG).

We therefore propose a strategic clinical trial to compare an INI containing regimen versus a boosted PI regimen in patients with advanced HIV-infection. We aimed to demonstrate the non-inferiority of an INI containing regimen [bictegravir (B) /emtricitabine (F) /tenofovir alafenamide (TAF) QD] versus a boosted PI regimen [darunavir (D) /cobicistat(C) /emtricitabine (F) /tenofovir alafenamide (TAF) QD] in patients with advanced HIV infection. The superiority of the INI-based treatment group over the PI-based treatment group will be assessed in the event that non-inferiority is established.

This Statistical Analysis Plan (SAP) details the different populations of analysis and the statistical methodology that will be used to analyse the data. It describes the efficacy and safety variables and anticipated data transformations and manipulations, and other details of the analyses not provided in the study protocol. The analyses described are based upon the clinical study protocol Version 2.0 dated 16 June 2020. This SAP will be validated and signed before the primary endpoint analysis is performed.

1.2 PURPOSE OF THE ANALYSES

The main purpose of this analysis is to compare two different types of HIV treatments, in terms of effectiveness and improvement of side effects, for patients who are diagnosed with a more advanced HIV infection. Patients with advanced HIV infections are otherwise known as 'late presenters'. These analyses will assess the efficacy and safety of BIC containing regimen in comparison with the boosted PI containing regimen. Advanced HIV infection is defined by an AIDS-Defining-Events (ADE) and/or an absolute number of T CD4+ lymphocytes $\leq 200/\text{mm}^3$.

The statistical analyses of the primary and secondary endpoints will be performed after the database locked and cleaned. The analysis will include all randomised patients enrolled who received at least one dose of the study drugs.

2. STUDY OBJECTIVES AND ENDPOINTS

2.1 STUDY OBJECTIVES

2.1.1 Primary objective

The primary objective of this study is to demonstrate the non-inferiority of an INI containing regimen [bictegravir (B)/emtricitabine(F)/tenofovir alafenamide (TAF) QD] versus a boosted PI regimen [darunavir (D)/cobicistat (C)/emtricitabine (F)/tenofovir alafenamide (TAF) QD] in patients with advanced HIV infection, in terms of reducing the occurrence of a composite outcome including virological and clinical reasons.

2.1.2 Secondary objectives

The secondary objective of this study is to investigate the immunological and virologic response, tolerability, resistance development, discontinuation of therapy due to tolerability, quality of life (QoL) and IRIS incidence.

2.1.3 Exploratory objectives

The exploratory objective of this study is to assess whether virologic response is better predicted by deep sequencing rather than standard population sequencing.

2.2 ENDPOINTS

2.2.1 Primary endpoint/outcome

The primary endpoint is time to failure. Failure is defined as the first occurrence of any of the following components:

1. Virologic reasons

- a) Insufficient virologic response, either:
 - a. HIV-1 RNA reduction < 1 log 10 copies/mL at week 12, or
 - b. Viral load > 50 HIV-1 RNA copies/mL at week 48
- b) Viral rebound, which is subsequently confirmed at the following scheduled or unscheduled visit, defined as either:
 - a. Rebound of HIV-1 RNA to >200 copies/mL after having achieved HIV-1 RNA <50 copies/mL
 - b. Rebound of HIV RNA by >1 log 10 copies/mL from nadir value, for patients whose viral load has never been suppressed below 50 copies/mL

2. Clinical reasons

- a) Death related to HIV, AIDS, OI/severe BI or complications of therapy including IRIS
- b) Any new or recurrent AIDS defining event on, or after 28 days of therapy
- c) Any new serious non-AIDS defining event documented by the endpoint review committee (including severe BI, end stage liver disease, renal failure, cardiovascular event, and non-AIDS related malignant disease)
- d) Clinically relevant AEs of any grade or IRIS which require treatment interruption (lasting > 5 days) of INI or boosted PI therapy within the first 48 weeks after randomisation

Note: Discontinuation of BIC or boosted DRV followed by (within 5 days) continuation with another INI or PI, respectively, is not considered as a strategy failure or endpoint.

All clinical events will be validated as endpoints by the Clinical Endpoint Committee.

Clinical events are referenced in the appendices : Appendices 1 (AIDS-Defining Conditions), 2 (INSIGHT Serious Non-AIDS Events Criteria), 3 (INSIGHT Progression of HIV Disease Criteria) and 4 (Immune Reconstitution Inflammatory Syndrome Generic Criteria).

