2.4 Outcome measures/endpoints

2.4.1 Primary endpoint/outcome

- Time to failure, as the first occurrence of any of the following components:

1. Virological reasons

- a) Insufficient virological response, either:
 - a. HIV-1 RNA reduction < 1 log 10 copies/mL at week 12, or
 - b. Viral load > 50 HIV-1 RNA copies/mL at week 48
- b) Viral rebound, which is subsequently confirmed at the following scheduled or unscheduled visit, defined as either:
 - a. Rebound of HIV-1 RNA to >200 copies/mL after having achieved HIV-1 RNA <50 copies/mL
 - b. Rebound of HIV RNA by >1 log 10 copies/mL from nadir value, for patients whose viral load has never been suppressed below 50 copies/mL

2. Clinical reasons*

- a) Death related to HIV, AIDS, OI/severe BI or complications of therapy including IRIS
- b) Any new or recurrent AIDS defining event on, or after 28 days of therapy
- c) Any new serious non-AIDS defining event documented by the endpoint review committee (including severe BI, end stage liver disease, renal failure, cardiovascular event, and non-AIDS related malignant disease)
- d) Clinically relevant AEs of any grade or IRIS which require treatment interruption (lasting > 5 days) of INI or boosted PI therapy within the first 48 weeks after randomisation

Note: Discontinuation of BIC or boosted DRV followed by (within 5 days) continuation with another INI or PI, respectively, is not considered as a strategy failure or endpoint.

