6.5 Withdrawal criteria

A subject is free to withdraw from the study at any time. In addition, the Investigator may decide, for reasons of medical prudence, to stop study medication (e.g. lack of efficacy).

All patients who discontinue study medication will be followed up and encouraged to attend for study visits up until week 48.

If this is not possible or acceptable to the subject or Investigator, the subject may be withdrawn from the study and the reason for withdrawal recorded in the Case Report Form (CRF).

Study medication may also be discontinued in the following instances:

1. If the subject withdraws their consent.
2. If the investigator considers in the interest of the subject (i.e. intercurrent illness, unacceptable toxicity) that it is best for them to stop study medication.
3. The subject fails to comply with the protocol requirements or fails to cooperate with investigator.
4. Pregnancy during the study (for patients receiving B/F/TAF, the study medication must be discontinued).
5. Discontinuation of the study at the request of the Sponsor, regulatory agency, or an IRB/IEC.

The date and reasons for stopping medication will be clearly stated on the subject's CRF and source document. Every attempt should be made to arrange follow up visits for subjects who are withdrawn from study medication. This visit should involve assessments as outlined in Appendix 1.

Subjects withdrawing from the trial should be offered alternative treatment as per the local standard of care by the Investigator.

Additional subjects may be recruited to account for any withdrawals should this be deemed necessary by the statistician or CI.

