7.5 Dosage modifications

Please refer to section 6.5 for withdrawal and stopping rules.

Treatment modification will be captured as a secondary endpoint only and modifications will be based on the treating physician's judgement.

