Virologic outcome will be determined by the last available measurement while the participant is on treatment and continues on trial within the time window. The time window for each timepoint is defined in Table A below.

Table A: Proposed Windows

Visit	Window (Through End-of-Study Week)	Window (Days)
24	18-30	127-210
36	30-42	211-294
48	42-54	295-378

Descriptive statistics and graphical representation

The analyses will be performed with the mITT population and DPS1. Data will be summarized with the number and percentage of participants with an event.

The proportion of patients with HIV-RNA viral load <50 copies/mL, HIV RNA viral load \geq 50 copies/mL, discontinuation due to Adverse Event (AE/SAE), discontinuation due to other reasons or on study but missing data at analysis time point will be calculated. The evolution over time will be analysed graphically using trend analysis.

HIV-RNA \geq 50 copies/mL includes: patients who changed any component of background therapy to a new drug class, changed background components that were not permitted per protocol, or changed any background drug in the regimen because of lack of efficacy (perceived or documented) before Week 48; patients who discontinued study drug or study before Week 48 for lack or loss of efficacy and patients who are equal to or above 50 copies/mL in the 48-week window.

AE/SAE includes: patients who discontinued because of adverse event (AE) or death at any time point from baseline through the time window if this resulted in no virologic data during the specified window.

Other Reasons includes: withdrew consent, loss to follow-up, moved, among others.

Statistical methodology

The proportion of patients with HIV-RNA viral load <50 copies/ml, HIV-RNA viral load \geq 50 copies/ml, discontinuation due to adverse event (AE/SAE), discontinuation due to other reasons or participating in the study but with missing data at the time of analysis will be calculated by dividing the number of participants with an event of interest by the total number of participants in the mITT population.

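### The primary analysis has two conflicting data rules after treatment is stopped, and under either one some patients stopped for insufficient virological response between weeks 12 and 48 are never primary events

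*Combined protocol and SAP*

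**What the plan says.** SAP 2.2.1 and 7.1, and Protocol v5.0 2.4.1 and 6.7, give the same virological triggers: "HIV-1 RNA reduction < 1 log 10 copies/mL at week 12, or" "Viral load > 50 HIV-1 RNA copies/mL at week 48", together with "Viral rebound, which is subsequently confirmed at the following scheduled or unscheduled visit, defined as either" of two patterns (above 200 after suppression below 50, or more than 1 log10 above nadir in those never suppressed). No threshold applies at weeks 24 or 36.

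The only treatment stop in the composite is "Clinically relevant AEs of any grade or IRIS which require treatment interruption (lasting > 5 days) of INI or boosted PI therapy". A Note in SAP 2.2.1 adds that moving within 5 days to another drug of the same class is not an endpoint.

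Stops for poor response are foreseen. Protocol v5.0 6.5 says that "the Investigator may decide, for reasons of medical prudence, to stop study medication (e.g. lack of efficacy"). Protocol v5.0 7.5 says: "Treatment modification will be captured as a secondary endpoint only". SAP 10.1.4 analyses stops or changes for insufficient virological response as a separate secondary endpoint.

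Two rules then govern data after a stop. The statistical methodology in SAP 7.1 censors virological evaluation when treatment is discontinued. SAP 5.2.1 assigns the primary endpoint to DPS1, which retains every observation whether or not drug was stopped or rescue given, and SAP 7.1 itself repeats that assignment.

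The snapshot analysis in SAP 7.2.2 classes as 50 copies/mL or more those "patients who discontinued study drug or study before Week 48 for lack or loss of efficacy".

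**The concern.** A patient whose regimen is abandoned because the virus is not controlled has failed the strategy in the ordinary sense, yet may never enter the primary analysis as an event. If virological follow-up is cut at the stop, Cox and Kaplan-Meier methods assume that the patient's later risk matches that of patients still on drug, although the stop was made because of viraemia. If all data are kept, the success of a rescue regimen can be credited to the randomised one. The trial is open-label (Protocol v5.0 6.1.5) and these stops are investigator decisions, so their frequency could differ by arm. A difference would bias the hazard ratio on which non-inferiority is judged.

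**Working it through.** **Step 1: run cases through the text.** Take a baseline viral load of 6.0 log10, 3.5 at week 12 and 3.0 at weeks 24 and 36, with drug stopped at week 36 for lack of efficacy. The week 12 fall is 6.0 − 3.5 = 2.5 log10, so that trigger is not met. There is no rise from nadir, so there is no rebound. Cases A and B differ in what follows. Cases C and D are rebounds above 200 after suppression, followed by a stop.

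| Case | SAP 7.1 censoring sentence | DPS1 | Snapshot, week 48 |
|---|---|---|---|
| A: below 50 on rescue at week 48 | censored for virological events at week 36 | no event | ≥50 |
| B: above 50 on rescue at week 48 | censored for virological events at week 36 | event at week 48 | ≥50 |
| C: next value, off drug, still above 200 | confirming value not used, no event | event | ≥50 if the reason is lack or loss of efficacy |
| D: no later viral load | no event | no event | as for C |

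The two rules disagree on B and C. Neither counts A or D.

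**Step 2: does the planned sensitivity analysis help?** It uses the per-protocol set with DPS2 (SAP 5.2.2), which drops observations after a stop, so it behaves like the censoring sentence. Protocol v5.0 9.3 would instead remove such patients from the per-protocol set, because they stopped for a reason that is not a primary component. Neither version counts them as failures.

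**Step 3: reproduce the design (SAP 4).** Margin: ln(0.63)/ln(0.75) = 1.606. Expected hazard ratio: ln(0.77)/ln(0.75) = 0.909. Events: 4(1.960 + 0.842)²/(ln 1.606 − ln 0.909)² = 96.9, so 97. Subjects: 97/0.24 = 404. The stated figures are right; the issue is what counts as an event.

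**Step 4: size, by assumption.** The documents give no rate of such stops.

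(a) Add uncounted stops to the planned 23% (INI) and 25% (PI), with HR = ln(1 − pINI)/ln(1 − pPI):
- 1% INI, 3% PI: ln(0.76)/ln(0.72) = 0.835
- 3% INI, 1% PI: ln(0.74)/ln(0.74) = 1.00
- 1% in both: ln(0.76)/ln(0.74) = 0.911
- 2% in both: ln(0.75)/ln(0.73) = 0.914

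(b) Suppose that the planned rates already include these stops and that 1, 2, 3 or 5% of patients in each arm go uncounted. With 202 per arm, events fall from 97 to 93, 89, 85 or 77, and power from 80% to 78.9, 77.6, 76.3 or 73.5%.

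(c) Suppose that the truth is at the margin (37% against 25%) and failures go uncounted in the INI arm only. The chance of declaring non-inferiority is Φ[(ln 1.606 − ln HR)√(D/4) − 1.96], where HR is the apparent hazard ratio and D = 202(pINI + pPI).

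| Uncounted, INI only | Apparent HR | D | Chance of declaring non-inferiority |
|---|---|---|---|
| 0% | 1.606 | 125.2 | 2.5% |
| 1% | 1.551 | 123.2 | 3.9% |
| 2% | 1.497 | 121.2 | 5.8% |
| 3% | 1.444 | 119.2 | 8.4% |
| 5% | 1.341 | 115.1 | 16.1% |

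With equal loss of 1 to 5% in both arms at the margin, the chance is 2.1% falling to 1.0%. Only a difference between arms inflates it.

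**The case against.** A reader might infer that every such patient is carried to week 48 as failure-free, whichever data set is used. The documents do not support that. Under the SAP 7.1 sentence the patient is censored for virological events. Under DPS1, a value above 50 at week 48 on any regimen counts. The rebound rule asks for confirmation at the next visit without requiring the patient to be on drug. Patients who stop drug are encouraged to attend to week 48 (Protocol v5.0 6.4 and 6.5), and for those who leave the study an early termination value can fill the nearest missing visit (SAP 5.3). Patients who met the week 12 trigger or had a confirmed rebound before stopping are already events.

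It is also tempting to read the disagreement with the snapshot as proof of a wrong primary definition. It is a different algorithm serving one of 13 secondary endpoints, none labelled the main one. The composite is the same in protocol v1.5, v5.0 and the SAP, and Protocol v5.0 7.5 deliberately keeps treatment modification out of it. Adding every stop or change for poor response would also collide with the within-class Note and would bring a subjective reason into components now set by laboratory thresholds.

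The numbers have limits too. The 25% rests partly on 20% virological failure in an earlier trial whose definition is not shown and may already include such stops. The formulas in Step 4 treat the uncounted stops as non-events, not as censored. Even at a hazard ratio of 1.00, 97 events give an expected upper limit of exp(1.96 × 2/√97) = 1.49, below 1.606.

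All of this stands, and it narrows the point. It does not reconcile the two data rules or make either count cases A and D.

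**Conclusion.** The point holds in a limited form. The SAP applies two incompatible rules to virological data after a stop. Under one, stops for insufficient response are informative censoring for virological events; under the other, only patients who resuppress on rescue end failure-free. A last rebound with no later usable viral load is missed under both.

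The size is unknown. If uncounted stops differ by two percentage points between arms, the planned 0.909 becomes 0.835 or 1.00. If they are equal, it stays at about 0.91 and the cost is a modest loss of power. No direction of bias can be claimed from the documents; an inference that the plan favours the INI arm would need a between-arm difference that they do not give. This is a low-cost improvement, not a fault in the sample size or in the composite itself.

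**What to change.** In SAP 7.1, reconcile the censoring sentence with DPS1 so that one rule governs the primary analysis. State whether composite follow-up continues for clinical events after a stop. Do not treat a stop for insufficient virological response as non-informative censoring.

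Prespecify an analysis, at minimum a sensitivity analysis of the primary Cox model reported beside it for the non-inferiority conclusion, that counts as virological failure:

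1. a stop of the randomised INI or PI strategy with insufficient virological response as the recorded reason, dated at the stop, supported by the viral-load series, and excluding same-class switches within 5 days under the SAP 2.2.1 Note;
2. a last rebound meeting item 1(b) of SAP 2.2.1 with no later viral load because the regimen was stopped or the patient left, dated at the rebound sample.

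Align the protocol and SAP per-protocol definitions for these patients at the same time.

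The cost is small. Stop dates and reasons are already recorded (Protocol v5.0 6.5) and analysed (SAP 10.1.4), and SAP 5.1 allows updates before sign-off. The downside is that item 1 depends on an investigator-recorded reason in an open-label trial. Making these items part of the primary definition, instead of a sensitivity analysis, may need a protocol amendment under Protocol v5.0 9.8.
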